### 3.2.5 Treatment Compliance

Treatment compliance is defined as the number of administered doses of AZD9291 (80 mg and 40 mg pooled) taken as a proportion of the scheduled expected number of doses.

## 4 ANALYSIS METHODS

### 4.1 General principles

The below mentioned general principles will be followed throughout the study:

- Descriptive statistics will be used for all variables, as appropriate. Continuous variables will be summarised by the number of observations (n), mean, standard deviation, median, minimum, and maximum. Categorical variables will be summarised by frequency counts and percentages for each category.
- For continuous data the mean and median will be rounded to 1 additional decimal place compared to the original data. The standard deviation will be rounded to 2

additional decimal places compared to the original data. Minimum and maximum will be displayed with the same accuracy as the original data.

- For categorical data, percentages will be rounded to 1 decimal place.
- SAS® version 9.3 or higher will be used for all analyses.
- As the only population considered will be the FAS, all tables, listings and figures (demographics, efficacy, safety, etc.) will be provided using this population, unless indicated otherwise.
- For time interval analyses in months, duration in months will be calculated as total duration in days/30.4375

#### 4.1.1 Handling missing data

In general, other than for partial dates, missing data will not be imputed and will be treated as missing.

#### **Imputation of partial dates**

##### **Initial diagnosis date:**

- If year is missing (or completely missing), do not impute.
- If only day is missing, impute day as 15th of the month.
- If day and month are missing, impute as July 1st.

##### **Concomitant medication start date**

- If year is missing (or completely missing), do not impute.
- If (year is present and month and day are missing) or (year and day are present and month is missing), impute as January 1st.
- If year and month are present and day is missing, impute day as first day of the month.

##### **Concomitant medication end date**

- If year is missing (or completely missing), do not impute.
- If (year is present and month and day are missing) or (year and day are present and month is missing), impute as December 31st.
- If year and month are present and day is missing, impute day as last day of the month.

## 4.2 Analysis Methods

### 4.2.1 Patient disposition

The total number of patients screened, enrolled and screen failed will be summarised. In addition, the number of patients in the FAS will also be provided.

The number and percentage of patients who have discontinued treatment and the main reason for discontinuation, the number and percentage of patients who transitioned to commercial

drug, as well as the number and percentage of patients who have completed or withdrawn from the study and the main reason for completion or withdrawal will be also presented.

#### 4.2.2 Protocol Deviations

All identified major protocol deviations will be listed and summarised for the FAS. All protocol deviations will be defined by the study team and identified and classified as major or minor before database lock.

#### 4.2.3 Demographics and other baseline characteristics

Demographic and baseline patient characteristics defined as data prior to the first AZD9291 dose (Demography, Receptor status, Lung cancer disease characteristics, Evaluation of brain/leptomeningeal metastases, which may be based on a scan taken within 28 days after the first dose (Please note: the delayed baseline assessment may introduce errors in the reported number of patients with brain/leptomeningeal metastases at baseline due to an early response to the treatment, or early progression in the site of brain/leptomeningeal.), Previous cancer therapy, Weight, WHO performance status, Electrocardiogram, Ophthalmologic assessment) will be summarised for the FAS.

In addition, the number (%) of patients by country of enrolment and by race (Asian vs non-Asian) will be summarised.

For receptor status the number (%) of patients positive for T790M only, the number (%) of patients positive for T790M + 1 other mutation, the number (%) of patients positive for T790M + 2 other mutations, the number (%) of patients positive for T790M + 3 other mutations, the number (%) of patients positive for T790M + 4 other mutations and the number (%) of patients positive for T790M + 5 other mutations will be summarised.

Specific mutation combinations will also be summarised.

In addition, the following subgroups will be identified and number (%) for each subgroup will be summarised:

- T790M only
- Common mutations: T790M + Exon 19 Deletion only  
T790M +L858R only
- Uncommon/ Compound mutations:
  - o Uncommon mutation T790M + G719X only  
T790M + S768I only  
T790M + Exon 20 Insertion only
  - o Common compound mutations: T790M + 2 common mutations
  - o Uncommon compound mutations: T790M + 2 or more mutations including at least 1 uncommon mutation

In this analysis patients classified as not detected or not done for a particular mutation will be regarded as not having the mutation.

Receptor status will also be summarised by brain/leptomeningeal metastases status at screening (Present; Absent, Not Done), by sample type (Plasma; Tissue; Other) and by prior

type of therapy (TKI alone; TKI + Other anti-cancer therapy including any anti-cancer treatment other than a TKI, palliative radiotherapies and surgery associated with advanced lung cancer as defined in Appendix 6).

Previous anti-cancer treatments will be summarised by category: TKI, Chemotherapy, Immunotherapy, Antiangiogenic therapy, Other anti-cancer treatment.

Lists of possible TKIs, Chemotherapy agents, Immunotherapy agents and Antiangiogenic therapies are provided in Section 9. All other anti-cancer treatments that are not listed in Section 9 are considered in the Other therapies category.

Previous radiotherapies and previous surgeries will also be summarised.

Previous surgeries will be summarised by category: associated with advanced lung cancer: not associated with advanced lung cancer.

List of surgeries associated with advanced lung cancer is provided in Section 9. All other surgeries not listed in Section 9 are considered as not associated with advanced lung cancer.

Additionally, the following derived variables will be summarised:

- Age at study enrolment as a continuous variable
- Age at study enrolment by class ( <50; >=50 - <65; >=65 - <75; >=75 - <80, >=80 and <65; >=65)
- Duration from most recent receptor status assessment for T790M mutation to study enrolment (months)
- Duration from original lung cancer disease diagnosis to study enrolment (months)
- Duration from last TKI exposure to study enrolment (<= 6 months, > 6 months)
- Duration from last dose of prior cancer therapy to study enrolment (months)
- Duration from scan for evaluation of brain/leptomeningeal metastases to study enrolment (months)
- Duration from last dose of prior anti-cancer therapy to most recent receptor status for T790M mutation (months)

Enrolment date corresponds to the date enrolment ID and AZD9291 are allocated to the subject in Interactive Web Response System (IWRS). Enrolment date may be prior to first dose date of AZD9291.

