**Subgroup Analyses**

Demographics, OS, PFS, TTD and RR will be analysed in the following subgroups of the FAS:

Subgroup	Demo-graphics	OS	PFS	TTD	RR
• Sex (male ; female)	√	√	√	√	√
• Age at enrolment (<75 ; ≥75 years of age)	√	Summary of cause of death	√	√	√
• Race (White, Black, Asian, and Other).	√		√	√	√
• Ethnicity (Asian, non-Asian).	√	√	√	√	√
• Country of enrolment	√		√	√	√
• WHO Performance Status (<2; =2)	√	√	√	√	√

Subgroup	Demo-graphics	OS	PFS	TTD	RR
• Prior Lines of therapy (one line ; more than one line)	√		√	√	√
• Mutation combinations as defined in section 4.2.3: (T790M only ;Common mutations Uncommon / Compound mutations)	√		√	√	√
• Mutation Status (Any compound mutations with a sample size of at least 50 patients (n≥50))	√		√	√	√
• Sample Type for receptor status assessment (Plasma ; Tissue ; Other)	√	√	√	√	√
• Type of T790M testing (Roche cobas® test on plasma ; Every other test on plasma with at least 50 patients ; Roche cobas® test on tissue ; Every other test on tissue with at least 50 patients)	√		√	√	√
• Brain/leptomeningeal metastases status at baseline (Present ; Absent ; Not Done)	√	√	√	√	√
○ Prior radiotherapy (Y/N) in Brain/leptomeningeal metastases subgroup	√		√		√
• Prior Type of anti-cancer therapy (TKI alone  ; TKI + Other anti-cancer therapy  )	√	√	√	√	√
• Prior Type of TKI (TKI first generation only ; TKI second generation only ; TKI first generation + TKI second generation, TKI first generation and/or second generation + TKI third generation)	√		√	√	√
• Prior chemotherapy (Yes  ; No)	√	√	√	√	√
○ Line of Chemotherapy (First line; Second line; Third line or more)	√		√	√	√

TKI alone does not refer to monotherapy, but only ever having previously received a TKI and no other anti-cancer treatment in the metastatic setting.

 Other anti-cancer therapy includes any anti-cancer treatment other than a TKI, palliative radiotherapies and surgery associated with advanced lung cancer as defined in Appendix 6.

 Subgroup Prior chemotherapy = Yes includes all patients previously treated by chemotherapy other than adjuvant or neo-adjuvant only.

Subgroup	Demo-graphics	OS	PFS	TTD	RR
• Use of TKI in patients with prior first or second line chemotherapy (Yes; No)	√		√	√	√

The subgroup analyses will be based on the values recorded on the CRF.

The subgroup analyses for time-to-event endpoints will be performed only for the subgroups with 20 events or more.

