##### ***Subgroup analyses***

Overall summary of AESIs and SAEs will be analysed in all subgroups of the FAS as defined in section 4.2.8 of the SAP.

[figure not shown]
[figure not shown]
A summary table of AEs with CTCAE grade  $\geq 3$  providing the number (%) of patients experiencing any of the specified terms will be also produced.

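### Brain/leptomeningeal status labelled baseline may come from a scan up to 28 days after first dose, so for late-scanned patients subgroup membership depends partly on post-treatment outcome

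*SAP*

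**What the plan says.** SAP 4.2.3 opens with a general rule: "Demographic and baseline patient characteristics defined as data prior to the first AZD9291 dose". Within the same sentence it exempts brain/leptomeningeal status, "which may be based on a scan taken within 28 days after the first dose". It then warns that "the delayed baseline assessment may introduce errors in the reported number of patients with brain/leptomeningeal metastases at baseline", and gives the mechanism as "due to an early response to the treatment, or early progression in the site of brain/leptomeningeal".

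The variable is used in these places:

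- **Efficacy subgroups (SAP 4.2.7, Subgroup Analyses).** The section states that "Demographics, OS, PFS, TTD and RR will be analysed in the following subgroups of the FAS". The row "Brain/leptomeningeal metastases status at baseline (Present ; Absent ; Not Done") is ticked in all five columns. A nested row for prior radiotherapy among patients with such metastases is ticked for demographics, PFS and RR.
- **Safety subgroups (SAP 4.2.8).** The overall AE summary is split by the same three categories. The addendum (4.1.2) carries this forward: "Overall summary of AESIs and SAEs will be analysed in all subgroups of the FAS as defined in section 4.2.8 of the SAP".
- **CNS findings at progression (SAP 4.2.7).** These are tabulated separately for patients with and without metastases at screening. This appears to be the same variable under another label.

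On the source of subgroup values, the SAP says only that "The subgroup analyses will be based on the values recorded on the CRF". OS, PFS and TTD are all counted from first dose (SAP 3.1.1 to 3.1.3).

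**The concern.** A subgroup factor should be fixed before the outcome starts to accrue. Here a patient's category can be set by a scan taken after up to four weeks of treatment. The SAP itself says that what happens in those weeks can change the category. A patient whose brain lesions have cleared can be recorded as Absent, and a patient with a new CNS lesion can be recorded as Present. A patient who dies before a planned late scan has no status and would presumably fall under Not Done.

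The SAP's warning covers only the count of patients with metastases. It does not extend to the subgroup medians, event rates and response rates built on the same classification. Those results would be published under a baseline label that the SAP's own definition contradicts. In the table of CNS findings at progression, a lesion that first appeared by day 28 and was recorded as Present would leave the group without metastases at screening, so new CNS involvement in that group would be understated.

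**Working it through.** **1. Is there a restriction elsewhere?** In the visible text there is none. The subgroup section takes CRF values as they stand. There is no landmark analysis, no analysis limited to pre-dose scans, and no rule that moves post-dose scans to Not Done. (The interim-analysis section is largely redacted and cannot be checked.) Protocol Table 4 places disease characteristics at screening, and Protocol section 5 lists brain/leptomeningeal metastases there as a baseline item. Neither states a post-dose allowance for this item.

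**2. Can the reader see how often it happens?** Only in part. SAP 4.2.3 summarises the time from the brain scan to enrolment, but also notes that enrolment may precede first dose. A scan dated after enrolment is therefore not necessarily a post-dose scan.

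**3. Survival window.** Inputs: 28 days (SAP 4.2.3), 30.4375 days per month (SAP 4.1), median OS 21 to 25 months and exponential OS (SAP 1.3). To confirm how the plan's OS figures are built, the 95% CI for 1983 events and a 25-month median is 25 × exp(±1.96/√1983) = 23.92 to 26.12 months, against the stated 23.9 to 26.1.

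- Window: 28 / 30.4375 = 0.92 month.
- As a share of median OS: 0.92/25 = 3.7%; 0.92/21 = 4.4%.

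This is the maximum, reached only by a patient scanned on day 28. It guarantees survival only. A patient can progress outside the CNS or stop treatment before the scan, so it does not guarantee time free of a PFS or TTD event.

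**4. Illustration for response rate.** The documents give none of the inputs below; all are assumptions.

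- f: share of patients with only a post-dose scan, 5% to 30%.
- p: true prevalence of brain/leptomeningeal metastases, 30% to 40%.
- c: share of truly Present patients who clear before the late scan, 10% to 30%.
- q: share of truly Absent patients with a new lesion by the late scan, 2% to 5%.
- r: true response rate, 60% in both groups, so the true difference is zero.
- Cleared patients all count as responders and new-lesion patients all as non-responders.

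Formulas:

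- Observed Present share: P = p(1 − fc) + (1 − p)fq.
- Observed Absent share: A = (1 − p)(1 − fq) + pfc.
- Observed RR in Present: (pr − pfc)/P.
- Observed RR in Absent: ((1 − p)r + pfc)/A.

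Low end (f = 0.05, p = 0.3, c = 0.1, q = 0.02):

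- P = 0.2992 and RR = 0.1785/0.2992 = 59.7%.
- A = 0.7008 and RR = 0.4215/0.7008 = 60.1%.
- Spurious difference about 0.5 point.

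High end (f = 0.30, p = 0.4, c = 0.3, q = 0.05):

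- P = 0.373 and RR = 0.204/0.373 = 54.7%.
- A = 0.627 and RR = 0.396/0.627 = 63.2%.
- Spurious difference about 8 points.

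The range shows only that the effect could be negligible or visible, depending on inputs that the documents do not give.

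**5. Direction for the other endpoints.** Moving early CNS progressors out of Absent would tend to make Present look worse and Absent better. Moving early responders into Absent improves Absent only if they do better than the average truly Absent patient. For OS, a patient with brain metastases may do worse than that even after an early response. For PFS, a lesion first seen after dosing, with no earlier brain scan to compare, may not be called progression at all. The survival requirement acts on late-scanned Present and Absent patients alike, so it separates both from Not Done more than from each other.

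**The case against.** The strongest reply has four parts.

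- **Disclosure.** The SAP states the delayed window and its mechanism where the variable is defined. This stands, but the disclosure stops at the patient count.
- **Limited consequence.** Protocol 9.4 says no tests will be performed. The visible text specifies no formal comparison between subgroups, and the overall OS, PFS, TTD and RR estimates do not use this variable. The safety use is one overall summary. All of this stands and limits the point.
- **Rarity.** The SAP only permits a late scan, and full clearance of CNS lesions within 28 days may be uncommon. This may be so, but the documents give no figure either way.
- **Cost in information.** Removing every post-dose scan from the classification could discard mostly correct readings. This is a fair reason to show both definitions rather than replace one with the other.

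A reader might also infer something stronger. Under exponential times, 2.5% to 3.0% of all patients would die within 28 days (OS medians 25 and 21 months), and 6.4% would progress or die (1 − 2^(−0.92/9.6), with the 9.6-month median PFS quoted in the protocol). It is tempting to treat these as the patients who can be misclassified. The documents do not support that:

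- The rates cover the whole analysis set, whereas a patient with a pre-dose scan cannot be reclassified. If 5% to 30% had only a post-dose scan (an assumption) and the same death rate applied, deaths by day 28 among them would be about 0.13% to 0.9% of the set (0.05 × 2.5% to 0.30 × 3.0%).
- Progression outside the CNS does not change brain status.
- Early responders are not counted in the 6.4%, so it is not an upper bound.
- The plan assumes exponential times for OS only, and the 9.6 months is a preliminary figure at 30% maturity from another study.

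Setting the 28-day window against median PFS would be wrong for the reason given in step 3 of the working.

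**Conclusion.** The point holds as stated in the heading. For patients whose only brain scan followed first dose, the subgroup label is partly a post-treatment outcome, while OS, PFS and TTD are counted from first dose. The guaranteed survival time is at most 0.92 month, or 3.7% to 4.4% of the assumed median OS.

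The size of the resulting bias cannot be fixed, because the share of post-dose-only scans is not given. For response rate the shift would tend to favour Absent; the 0.5 to 8 point range rests entirely on assumed inputs. A claim that the bias runs in one known direction for every endpoint would go beyond the documents. The overall estimates are unaffected.

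**What to change.** 1. Report the number of patients whose status rests only on a post-dose scan, with scan timing measured against first dose rather than enrolment.
2. Present the brain/leptomeningeal subgroup results using only scans dated on or before first dose, with post-dose-only patients in a separate category, alongside the current definition. Treat the split of CNS findings at progression in the same way.
3. Extend the existing caveat from the patient count to the efficacy and safety subgroup tables, including the addendum's AESI/SAE summary, and to the table of CNS findings at progression.

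The scan date is already used for the duration summary in SAP 4.2.3, so this is a change of derivation and needs no new data. The cost is one additional set of subgroup outputs, and fewer classified patients in the pre-dose-only version. It is a cheap improvement.

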## LIST OF ABBREVIATIONS AND DEFINITION OF TERMS

The following abbreviations and special terms are used in this Study Protocol.

Abbreviation or special term	Explanation
AE	Adverse event
AESI	Adverse Event of Special Interest
AZ	AstraZeneca
CI	Confidence Interval
CNS	Central nervous system
CRF	Case Report Form (electronic/paper)
CTCAE	Common Terminology Criteria for Adverse Event
CYP	Cytochrome P450
CT	Computer Tomography
DCO	Data cut-off
DLT	Dose limiting toxicity
ECG	Electrocardiogram
EGFR	Epidermal Growth Factor Receptor
EGFRm	EGFR Mutation positive; EGFR Sensitizing Mutation positive
GCP	Good Clinical Practice
GMP	Good Manufacturing Practice
IB	Investigator's Brochure
ICF	Informed Consent Form
ICH	International Conference on Harmonisation
ILD	Interstitial Lung Disease
ICMJE	International Committee of Medical Journal Editors
IP	Investigational Product
IVRS/IWRS	Interactive Voice Response System/ Interactive Web Response System
MedDRA	Medical Dictionary for Regulatory Activities
MRI	Magnetic Resonance Imaging
NSCLC	Non-Small Cell Lung Cancer
ORR	Objective response rate

Abbreviation or special term	Explanation
OS	Overall Survival
PFS	Progression Free Survival
PT	Preferred Term
QT	Interval on the electrocardiogram representing the duration of depolarization and repolarization of the heart
QTc	The QT interval corrected for heart rate
QTcF	QT interval corrected per Fredericia's formula
RECIST 1.1	Response Evaluation Criteria in Solid Tumors version 1.1
SAE	Serious adverse event
SOC	System Organ Class
SmPC	Summary of Product Characteristics
T790M	An amino acid substitution at position 790 in EGFR, from a Threonine (T) to a Methionine (M). Presence of T790M
TKI	Tyrosine Kinase Inhibitor
TTD	Time to treatment discontinuation
US	United States
WBDC	Web based data capture
WHO	World Health Organization

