### **3.1 Inclusion criteria**

For inclusion in the study patients must fulfill the following criteria:

1. Provision of signed and dated written informed consent by the patient or legally acceptable representative prior to any study-specific procedures
2. Adults (according to each country regulations for age of majority)
3. Locally advanced (stage IIIB) or metastatic (stage IV) EGFRm NSCLC, not amenable to curative surgery or radiotherapy, with confirmation of the presence of the T790M mutation
4. Prior therapy with an EGFR-TKI. Patients may have also received additional lines of treatment
5. World Health Organization (WHO) performance status 0-2
6. Adequate bone marrow reserve and organ function as demonstrated by complete blood count, biochemistry in blood and urine at baseline
7. ECG recording at baseline showing absence of any cardiac abnormality as per exclusion criterion #6
8. Female patients of childbearing potential must be using adequate contraceptive measures (see Restrictions, Section 4.2), must not be breast feeding, and must have a negative pregnancy test prior to start of dosing. Otherwise, they must have evidence of non-childbearing potential as defined below:
  - a. Post-menopausal defined as aged more than 50 years and amenorrheic for at least 12 months following cessation of all exogenous hormonal treatments
  - b. Women under 50 years would be consider post-menopausal if they have been amenorrheic for 12 months or more following cessation of exogenous hormonal

- treatments and with luteinizing hormone and follicle-stimulating hormone levels in the post-menopausal range for the institution
- c. Documentation of irreversible surgical sterilisation by hysterectomy, bilateral oophorectomy or bilateral salpingectomy but not tubal ligation
9. Male patients must be willing to use barrier contraception, i.e., condoms (see Restrictions, Section 4.2)

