## **4 ANALYSIS METHODS**

### **4.1.1 Efficacy**

#### ***Overall Survival (OS)***

Overall survival will be summarised by mutation combination subgroup.

Analysis will include the number of exposed patients, the number of deaths, the number of censored patients and the number of patients prematurely censored.

In addition, duration of follow-up will be summarised as defined in Section 4.2.7 of the SAP:

- In all censored patients;
- In prematurely censored patients;
- In all patients.

A swimmer plot for OS will be produced for the uncommon/compound mutation subgroup. The swimmer plot will include all patients with an uncommon/compound mutation and will be ordered by mutation combination. Median OS and 95% confidence intervals for Full Analysis

Set will be reported as reference lines. Censored patients will be identified by a cross at the time of censoring.

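### SAP 4.2.3 counts mutation tests that were not done as mutation absent, which may misclassify untested patients, chiefly in the 'T790M only' subgroup

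*SAP*

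**What the plan says.** SAP 4.2.3 sorts patients into 'T790M only', common mutations (T790M plus exon 19 deletion only, or plus L858R only) and uncommon/compound mutations. It then sets the coding rule, for this analysis, that patients classified as "not detected or not done for a particular mutation will be regarded as not having the mutation".

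The groups are carried forward in two places:
- The SAP 4.2.7 subgroup table lists "Mutation combinations as defined in section 4.2.3" for demographics, PFS, TTD and RR. OS is not ticked for this factor.
- Addendum 4.1.1 states: "Overall survival will be summarised by mutation combination subgroup". Its listed content is numbers exposed, deaths, censored and prematurely censored, and duration of follow-up.

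Three other provisions bear on the rule:
- SAP 4.1.1 sets a general default, with partial dates excepted, that "missing data will not be imputed and will be treated as missing".
- Brain/leptomeningeal status is handled differently in SAP 4.2.3 and 4.2.7: 'Not Done' is kept as its own level beside present and absent.
- Protocol 3.1, criterion 3, admits locally advanced or "metastatic (stage IV) EGFRm NSCLC, not amenable to curative surgery or radiotherapy, with confirmation of the presence of the T790M mutation". The protocol's abbreviation list expands EGFRm as "EGFR Mutation positive; EGFR Sensitizing Mutation positive".

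**The concern.** The rule merges two different states, tested with nothing found and not tested, although the case report form evidently records them separately.

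Untested mutations are foreseeable here. Protocol 4.1 (Table 4 note d, and item 3 under patient enrolment) requires T790M status after progression to be known before treatment. It does not ask for a result on each of the other mutations that SAP 4.2.3 lists. Testing is local wherever possible, and the SAP subgroup table expects several assays on plasma and tissue. Since entry requires EGFR-mutated disease, 'T790M only' is the group in which an untested sensitising mutation is most plausible.

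At stake is the meaning of the 'T790M only' rows for prevalence, PFS, TTD and RR. The unredacted text plans no count of not-done results, no category for untested patients and no check in fully tested patients. A reader of the report could not tell a biological group from a testing artefact.

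**Working it through.** The plan states no figure on this point, so there is none to reproduce. The check is misclassification arithmetic on assumed inputs, with not-done status taken as independent of true status.

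**'T790M only'.** Let p0 be the share of patients who would be 'T790M only' if every listed mutation were tested. Let u be the share with none of the other mutations tested. The documents give neither.
- Reported share = (1 − u)·p0 + u.
- Misclassified part of the reported group = u(1 − p0) / [(1 − u)·p0 + u].
- At p0 = 5%, u = 5%: reported share = 0.95 × 0.05 + 0.05 = 9.75%. Misclassified part = 0.05 × 0.95 / 0.0975 = 49%.

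The effect on RR needs an assumed outcome gap. Protocol 1.4.2 reports response rates of 50% to 70% in T790M-positive patients. Those two ends are borrowed only for scale: 50% in patients who would be 'T790M only' under full testing, 70% in the others. Reported RR = 50% + 20% × misclassified part.

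| u (p0 = 5%) | Reported 'T790M only' share | Misclassified part | Reported RR |
|---|---|---|---|
| 0% | 5.0% | 0% | 50.0% |
| 2% | 6.9% | 28% | 55.5% |
| 5% | 9.75% | 49% | 59.7% |
| 10% | 14.5% | 66% | 63.1% |
| 20% | 24.0% | 79% | 65.8% |

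The result depends strongly on p0. At p0 = 20% the misclassified part is 7%, 17%, 29% and 44% for u = 2%, 5%, 10% and 20%. If the two response rates are equal, the RR does not move, whatever u is. The mixture formula suits a proportion such as RR. It does not carry over to Kaplan-Meier medians, so no figure is offered for PFS or TTD.

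**Single common combinations** (for example T790M plus exon 19 deletion only). Let q be the share of carriers who have a further listed mutation and u the share not tested for it.
- Misclassified part = uq / [(1 − q) + uq].
- Lowest case, q = 1%, u = 5%: 0.0005 / 0.9905 = 0.05%.
- Highest case, q = 10%, u = 50%: 0.05 / 0.95 = 5.3%. With a 20-point gap in RR this is a shift of about 1 point.

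**Pooled uncommon/compound.** Membership needs a detected uncommon mutation or more than one detected mutation besides T790M. Coding untested as absent can remove a patient from this group or relabel one within it. It cannot bring in a patient in whom no such mutation was detected.

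**Primary OS in the full analysis set.** No mutation grouping enters it.

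**The case against.** The rule is explicit and confined to this analysis. The protocol (section 9.4) makes all analyses descriptive, without tests, so no error rate is at stake. The share of tests not done might be close to zero. All of that stands, and it limits the weight of the point.

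Four stronger readings are tempting, and the documents do not support them.

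- *The rule contradicts SAP 4.1.1.* That section is a general default. A later rule stated openly for one analysis is a disclosed exception, though an unexplained one.
- *The subgroup results are distorted, with differences diluted.* This needs some tests not done and an outcome gap between misclassified and correctly placed patients. Dilution further assumes that the untested behave like common-mutation patients. The documents establish none of these.
- *Patients tested and not detected are true negatives.* If EGFRm is read as sensitising-mutation positive, no eligible patient is truly 'T790M only'. Those left after full testing would be assay misses or eligibility deviations. No recoding yields a clean biological group. It can only stop untested patients being reported as if they had a result.
- *The swimmer plots and the OS results mix in untested patients.* Both swimmer plots (SAP 4.2.7 for PFS, Addendum 4.1.1 for OS) cover only the uncommon/compound group, which can only lose patients. The OS summary by mutation group is a set of counts and follow-up times, with no planned Kaplan-Meier comparison between groups. Its 'T790M only' row does inherit the classification.

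**Conclusion.** The point holds as a risk of misclassification, concentrated in 'T790M only'. For prevalence the direction is known: coding untested as absent can only enlarge that group, and it overstates the group whenever an untested patient carries another listed mutation. For PFS, TTD and RR neither direction nor size can be derived from the documents.

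The 49% figure illustrates the leverage that a few percent of untested patients have on a small group. It rests on p0 = 5%, u = 5% and independence, all assumed, and is not an estimate for this study. The small effect on single common combinations likewise holds only over the assumed ranges of q and u. The change is worth making as a cheap improvement to descriptive subgroup reporting.

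**What to change.** Amend SAP 4.2.3 and the subgroup table in 4.2.7 as follows:

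1. Report the number of patients with a not-done result for each listed mutation (exon 19 deletion, L858R, G719X, S768I, exon 20 insertion).
2. Restrict 'T790M only' to patients with a not-detected result for all the other listed mutations.
3. Show patients with no other mutation detected and at least one not done in a separate row, 'T790M, other mutations not fully tested'.
4. Leave patients with a detected common or uncommon mutation in their current groups. Moving everyone with any single missing test would empty groups where misclassification is probably small, and could select by laboratory or country if test panels differ.
5. Repeat the mutation-subgroup summaries in patients with a result for every listed mutation, as a sensitivity analysis.

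This needs a wording change and a derivation from data already collected. The cost is a few extra rows and a smaller 'T790M only' group. That group could fall below the 20 events that SAP 4.2.7 requires for time-to-event subgroup analyses, in which case its PFS and TTD would not be summarised.
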